10.3.2 Evaluation of serious adverse events and premature withdrawals

Adverse events deemed serious and those resulting in treatment withdrawal or death will be summarized separately. Narrative paragraphs will be generated to describe the circumstances surrounding each SAE and death.

10.3.3 Evaluation of laboratory parameters and assays

Selected clinical laboratory parameters will be summarized and clinically significant changes from baseline will be discussed.

10.3.4 Extent of exposure

Treatment exposure will be summarized for all patients, including dose administration, number of cycles, dose modifications or delays, and duration of therapy.

10.4 Statistical Procedures

Summary statistics include the number of observations, mean, standard deviation, median, minimum, and maximum values.

10.4.1 Sample size calculation

Based on the largest multi-institutional SRT series published (n=1,540) in which patients received SRT followed by observation until the PSA reached ≥ 0.2 ng/mL above the post-SRT nadir, the 2-year FFPP was approximately 60% with SRT. For our primary endpoint of 2-year FFPP we expect an absolute 20% improvement with the treatment of SRT+ enzalutamide (2-year FFPP 80%) over SRT alone (2-year FFPP 60%).

We originally assumed an accrual time of 18 months, with ≥ 24 months of additional follow-up time. FFPP at 2 year from 60% to 80%, a 20% increase (corresponding to a hazard ratio of 0.44 under the assumption of exponential distribution of event times) corresponds to 39 events total of PSA progression (for example 26 in Arm A, and 13 in Arm B) with a 90% power to detect an improvement of, using a one-sided log-rank test at significance level 0.1. Adjusting for 15% non-evaluable or dropout patients, we will randomize a total of 122 patients (61 patients in each arm).

The power of the study is driven by the number of PFS progression events. The design requires 39 events when the analysis of the primary endpoint is conducted. Under the assumption that there are not non-evaluable patients or no dropout, a total of 102 patients needs to be enrolled over 18 months with ≥ 24 months of additional follow-up to reach 39 events. Because the study duration is as long as 3.5 years, a fair number of patients may be lost to follow-up before that and their time to PSA progression will be censored at the last date of PSA measurement. So we assume a non-evaluable and loss-to-follow-up rate of 15% when we estimate the total number of participants.

The trial started enrolling patients in April 2015, and has enrolled 80 patients by April 2019. The rate of accrual is about 10 patients every 6 months. Due to slower than expected enrollment, we propose to extend the accrual time to the end of March 2020. We plan to conduct the primary analysis when 39 events occur.

Our new efficacy assumption stays the same as to detect the difference of Freedom From PSA Progression (FFPP) at 2 year from 60% in SRT+placebo arm to 80% in SRT+enzalutamide arm, a 20% increase (corresponding to a hazard ratio of 0.44 under the assumption of exponential distribution of event times.) The study power remains at 90% with one-sided type I error 0.1 using log-rank test.

The sample size is 96 total (48 per arm) accounting for 15% loss-to-follow up before PSA progression events. Below represents the new enrollment target for patients given this revised power calculation based on number of events thus far, follow-up and drop out to date.

Total number of PSA progression events	Sample size	Planned accrual time (mons)	Additional follow-up time (mons)	End of accrual	End of follow-up (start the analysis)	Power
Original design						
39	122 (61 per arm)	18	24			90%
New design						
39	96 (48 per arm)	60	21	March 2020	Dec. 2021	90%

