2. OBJECTIVES

2.1 Primary Objective

The primary efficacy endpoint is the rate of Freedom-from-PSA-progression (FFPP). FFPP is defined as the time from randomization to the date of PSA progression. A subject who does not have PSA progression at the time of the analysis will be censored at the last date of PSA measurement.

In patients who achieve an undetectable PSA value (defined as ≤ 0.1 ng/mL), PSA progression is defined as a detectable PSA value (≥ 0.2 ng/mL) that is confirmed by a second consecutive PSA value obtained ≥ 8 weeks later which is higher (and ≥ 0.4 ng/mL). In patients who do not achieve an undetectable PSA, PSA progression is defined as a 0.2 ng/mL increase from nadir that is confirmed by a second consecutive PSA value obtained ≥ 8 weeks later which is higher. The date of PSA progression will be defined as the first date of PSA rise from nadir or baseline.

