9.6 End of Study

This study will end and study database locked when 24 months of follow up is reached from the last patient being enrolled. A final study report will be provided within 3 months of the end of the study.

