10. STATISTICAL CONSIDERATIONS

10.1 Study Endpoints

10.1.1 *Analysis of the primary endpoint*

The study is a multi-center, double-blind, placebo controlled, randomized Phase II trial in patients with non-castrate PSA-recurrent prostate cancer after radical prostatectomy. Eligible patients will be randomized in a 1:1 ratio to one of two treatment arms: SRT *plus* placebo (Arm A) or SRT *plus* enzalutamide (Arm B). Randomization will be stratified by center, and surgical margin status (R0 vs R1), PSA prior to salvage treatment (PSA ≥ 0.5 vs < 0.5 ng/mL), and pathologic Gleason score (7 vs 8-10).

The primary objective of the study is to evaluate the efficacy of the two treatment regimens based on freedom-from-PSA-progression (FFPP). FFPP is defined as the time from randomization to the date of PSA progression. A subject who does not have PSA progression at the time of the analysis will be censored at the last date of PSA measurement. In patients who achieve an undetectable PSA value (defined as ≤ 0.1 ng/mL), PSA progression is defined as a detectable PSA value (≥ 0.2 ng/mL) that is confirmed by a second consecutive PSA value obtained ≥ 8 weeks later which is higher (and ≥ 0.4 ng/mL). In patients who do not achieve an undetectable PSA, PSA progression is defined as a 0.2 ng/mL increase from nadir that is confirmed by a second consecutive PSA value obtained ≥ 8 weeks later which is higher.

It is very unlikely deaths in the time frame of this trial will be from prostate cancer. Censoring the subjects that have died at the date of the last PSA measurement before death will be performed (as we will not know if PSA changes in the interval) unless there is clear evidence of death from prostate cancer per the treating physician and/or by autopsy.

FFPP will be summarized using Kaplan-Meier method by treatment arms. FFPP probability will be estimated using the Kaplan-Meier method. FFPP curves will also be displayed graphically. Differences in FFPP between treatment arms will be compared by the log rank test. The Cox proportional hazards regression model will be fitted, and the estimated hazard ratio (Arm B/Arm A) and corresponding 95% CI will be provided. Additionally, Cox regression models will be used to explore the potential influences of the other prognostic factors on the primary FFPP endpoints.

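### PSA rises still awaiting confirmation at the 39-event analysis are censored on their would-be event date, which slightly inflates the late FFPP curves

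*Combined protocol and SAP*

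**What the plan says.** - **Trigger.** Section 10.4.1: "We plan to conduct the primary analysis when 39 events occur". The table that ends that section puts the start of the analysis in December 2021, 21 months after accrual closes in March 2020.
- **Event.** Section 10.1.1 and several other sections require a second consecutive, higher PSA at least 8 weeks after the first. After an undetectable PSA, that second value must also reach 0.4 ng/mL.
- **Event date.** Section 2.1 only: "The date of PSA progression will be defined as the first date of PSA rise from nadir or baseline".
- **Censoring.** Section 10.1.1: "A subject who does not have PSA progression at the time of the analysis will be censored at the last date of PSA measurement".
- **PSA schedule.** Section 5.2 sets follow-up PSA every 3 months, give or take 1 month. Footnote 8 of Table 1 keeps a man on study until his confirmatory PSA is drawn.
- **Lock.** Section 9.6: "This study will end and study database locked when 24 months of follow up is reached from the last patient being enrolled".

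No section says how a rise that is still unconfirmed at the analysis is to be handled.

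**The concern.** The confirming PSA usually arrives about one visit after the first rise, but the event takes the date of the first rise. Event-free time is thus counted up to the analysis, while events are counted only up to about one visit before it. A man caught in between is censored because he has begun to progress, which makes the censoring informative. The plan reports Kaplan-Meier curves and FFPP probabilities by arm. Their tails would read too high, and progressions already observed would be missing from a small analysis. Without a written rule, the team would also have to decide what to do with these men when the data are already in hand.

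**Working it through.** **1. Reproduce the design.** Section 10.4.1 gives 2-year FFPP of 60% and 80%, a 90% power target, and a test "using a one-sided log-rank test at significance level 0.1".

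- Monthly hazards: −ln(0.6)/24 = 0.0213 (Arm A) and −ln(0.8)/24 = 0.0093 (Arm B). Ratio: ln(0.8)/ln(0.6) = 0.437; the plan states 0.44.
- Events (Schoenfeld): 4(1.2816 + 1.2816)²/(ln 0.44)² = 39, as stated.
- Power with 39 events: Φ(√(39/4) × 0.821 − 1.2816) = 0.900.
- Revised design, 60 + 21 months, 48 per arm: event probabilities 0.639 and 0.370. Expected events: 48 × (0.639 + 0.370) = 48.4, and × 0.85 = 41.1 after 15% loss. This is consistent with 39 by December 2021.

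**2. Men pending, by hand, at a fixed cut at month 81.** Pending ≈ men at risk × hazard × lag, with a lag of 3 months (one visit).

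- Arm A: 48 × (1 − 0.639) × 0.85 × 0.0213 × 3 = 0.94
- Arm B: 48 × (1 − 0.370) × 0.85 × 0.0093 × 3 = 0.72
- Total about 1.7, or 1.0 with an 8-week lag and 2.2 with a 4-month lag.

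**3. Curve bias, by hand.** With uniform accrual, follow-up at month 81 is uniform over 21 to 81 months. The cumulative hazard missed by time t is hazard × lag × ln(60/(81 − t)).

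- Arm A, t = 48: 0.0213 × 3 × ln(60/33) = 0.038. FFPP is overstated by 0.36 × (e^0.038 − 1) = 1.4 points.
- Arm A, t = 60: 0.0213 × 3 × ln(60/21) = 0.067, or 0.279 × (e^0.067 − 1) = 1.9 points.
- Arm B, same steps: 1.1 and 1.7 points.
- At t = 24: 0.2 (A) and 0.1 (B).

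**4. Simulation.** 96 men, exponential times, uniform accrual, 15% loss, PSA at months 2 to 6 and then every 3 months. Confirmation comes at the first visit at least 8 weeks later, and every rise is taken to be confirmed. With the cut at the 39th confirmed event (2,000 trials), a mean of 2.1 men are pending (1.25 in A, 0.88 in B), and 89% of trials have at least one.

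| FFPP (%) | As written | Pending counted | Difference |
|---|---|---|---|
| Arm A, 24 months | 60.8 | 60.0 | 0.8 |
| Arm A, 48 months | 37.9 | 35.7 | 2.2 |
| Arm A, 60 months | 31.5 | 28.6 | 2.9 |
| Arm B, 24 months | 80.6 | 80.1 | 0.5 |
| Arm B, 48 months | 65.3 | 63.7 | 1.6 |
| Arm B, 60 months | 59.6 | 57.0 | 2.6 |

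With a fixed cut at month 81, 1.7 men are pending. The differences are then 0.4, 1.5 and 2.0 points in Arm A, and 0.2, 1.2 and 1.8 in Arm B.

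**5. Effect on the test.** The median hazard ratio is 0.437 as written and 0.441 with pending rises counted. In 2,000 simulated null trials, rejection at the nominal 10% was 9.5% and 9.2%. Simulated power is 89.4% as written and 90.7% with the pending rises.

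**6. Sensitivity.** If confirmation takes two visits, 3.9 men are pending and the 60-month overstatement is about 5 points. If follow-up ends 42 months after randomization, about 0.9 men are pending, the overstatement at 36 months is about 0.9 (A) and 0.7 (B) points, and nobody is at risk at 60 months.

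**The case against.** Most of the case for leaving the plan alone is sound.

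- **Power.** A reader might infer that the trial loses two of its 39 events. The documents do not support this. An event is by definition a confirmed rise, so an analysis triggered at 39 events has all 39 and about 90% power. The other two are a surplus. Power would fall, to 88.8% with 37 confirmed events, only if unconfirmed rises were counted towards the trigger, and nothing in the plan says that they are.
- **Treatment effect.** A reader might infer a biased comparison. The log-rank test and the hazard ratio hardly move, and neither does the 2-year FFPP on which the design rests. The decision differs in 3.8% of simulated trials, but adding two events to a 39-event test can do that by itself, and the type I error does not change.
- **The 5-year figure.** No section specifies a 5-year FFPP. Only about 3 (A) and 6 (B) men are at risk at 60 months, with a standard error of 9 to 10 points against a bias of about 2.5.
- **The 42-month limit.** Sections 5.2 and 5.6 and footnote 9 of Table 1 mention PSA follow-up to 42 months. That equals 18 + 24 from the original design and may be left over from it. If it caps each man, the bias is under 1 point.
- **Confirmations may arrive anyway.** Footnote 8 keeps men on study, and the lock in section 9.6 falls 3 months after December 2021. But footnote 8 governs retention and not the data cut, and section 9.6 disagrees with section 10.4.1 on timing. Neither supplies a rule.

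What is left is a real gap in wording with a small, one-directional effect on the curves.

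**Conclusion.** The rules combine to censor a man on what would become his event date. About 2 observed progressions beyond the required 39 are left out. FFPP is overstated in both arms by about 0.5 points at 2 years, 1.5 to 2 at 4 years and 2 to 3 at 5 years, or by under 1 point if follow-up stops at 42 months per man. The primary test, the hazard ratio and the planned power stand, so this is a minor improvement and not a threat to the trial's conclusion.

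The size assumes exponential times, uniform accrual, a lag of about one visit, and that every pending rise is later confirmed. The documents give no confirmation rate, and a lower one would shrink the effect in proportion. Back-dating stands only in section 2.1. If its first rise can precede the qualifying value, the man is censored after his would-be event date instead of on it, but he is still lost as an event.

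**What to change.** In sections 10.1.1 and 10.4.1:

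1. Define the data cut-off as the date on which the 39th progression is confirmed, separate from the database lock.
2. Count a first qualifying PSA dated on or before the cut-off as an event on that date if the next PSA at least 8 weeks later confirms it. Use PSA values after the cut-off for nothing else.
3. Lock when all pending rises have been rechecked, or at a stated limit of about 5 months. Visits at 3 months ± 1 month can be 3 + 1 + 1 = 5 months apart. A 4-month limit is too short, because about 19% of simulated confirmations took longer. A few would exceed 5 months, when the next visit falls inside the 8 weeks.
4. Keep men whose rise is not confirmed, or never rechecked, as censored. Add one sensitivity analysis that counts those never rechecked as events.

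An alternative with no delay is to end each man's follow-up at the last PSA that could have been confirmed by the cut-off. This removes the bias but does not add the extra events.

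Either way, reconcile the lock in section 9.6 (24 months after the last enrolment) with the analysis date in section 10.4.1 (21 months), and state whether the 42-month limit applies to each man.

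The cost is a few sentences of wording and, for the main option, up to one long visit interval before lock. It needs no extra patients or tests.

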10.4.2 Stratification factors

Randomization will be stratified by center, and surgical margin status (R0 vs R1), PSA prior to salvage treatment (PSA ≥ 0.5 vs < 0.5 ng/mL), and pathologic Gleason score (7 vs 8-10).

10.4.3 Derived variables

- FFPP will be summarized using Kaplan-Meier method by treatment arms. FFPP curves will also be displayed graphically. Differences in FFPP between treatment arms will be compared by the log rank test. The Cox regression model will be fitted, and the estimated hazard ratio (Arm B/Arm A) and corresponding 95% CI will be provided.
- FFPP probability will be estimated using the Kaplan-Meier method
- Additionally, Cox regression models will be used to explore the potential influences of the other factors on the primary FFPP endpoints.
- Time-to-event endpoints time to local recurrence and radiographic MFS will be analyzed similarly as described for the FFPP.
- For safety analysis, overall safety profile and toleration of Arm A and Arm B will be characterized by type, frequency, severity, timing and relationship of study therapy of adverse events and laboratory abnormalities. Adverse events will be summarized by the frequency of patients experiencing treatment emergent adverse events corresponding to body systems and by worst NCI CTCAE (version 4.0) grade.

11. PROTECTION OF HUMAN SUBJECTS

11.1 Ethical Considerations

This study will be conducted in compliance with the protocol, GCP guidelines established by the International Conference on Harmonisation, and the ethical standards set forth in the Declaration of Helsinki 2004 (available at: www.laakariliitto.fi/e/ethics/helsinki.html).

11.2 Protocol Amendments

Before starting the study, the protocol must be approved by each institution's IRB or Independent Ethics Committee (IEC). Amendments to the protocol may be made only with consent of the lead site/sponsor and principal investigator and are subject to IRB approval before instituting.

11.3 Written Informed Consent

Before obtaining consent, members of the study team will review the rationale for the treatment program with the patient. The discussion will review the alternatives available (including hormonal therapy, chemotherapy, or supportive care as appropriate), the potential benefits of this program, the risks and the probability of their occurrence, and the procedures to minimize these risks. Should an adverse event occur, the provisions available to ensure medical intervention will also be reviewed. Why the risks are reasonable in relation to the anticipated benefits, incentives, or costs that will or may be incurred as a result of participating in the study, as well as the efforts to maintain confidentiality, will also be discussed with the patient.

Patients will be required to sign and date (in triplicate) a statement of informed consent that meets the requirements of the Code of Federal Regulations (Federal Register Vol. 46, No. 17, January 27, 1981, part 50) and the IRB. The medical record will include a statement that written informed consent was obtained (and document the date that it was obtained) before the patient is enrolled in the study. The original signed document will become part of the patient's medical record, a copy will be forwarded to the lead site/sponsor pursuant to sponsor registration and to the PCCTC coordinating center at MSKCC, and a copy will be sent home with each patient.

The consent form will include the following:

- the nature and objectives, potential toxicities, and benefits of the intended study
- the length of therapy and likely follow-up required
- alternatives to the proposed therapy (including available standard and investigational therapies)
- the name of the investigator(s) responsible for the protocol
- the right of the patient to accept or refuse treatment and to withdraw from participation in this study
- Text regarding the consortium and the coordinating center should be added to all institutional informed consent documents and sections in the research authorization/HIPAA forms (eg, "Prostate Cancer Clinical Trial Consortium, Coordinating Center at Memorial Sloan-Kettering Cancer Center, New York, NY")

11.4 Protection of Privacy

Patients will be informed of the extent to which their confidential health information generated from this study may be used for research purposes. After this discussion, they will be asked to sign a Notice of Privacy Practice research authorization/HIPAA form. The original signed documents will become part of the patient's medical records, and each patient will receive a copy of the signed documents. The use and disclosure of protected health information will be limited to the individuals described in the research authorization

form. The research authorization form must be completed by the principal investigator and approved by the IRB.

11.5 Terminating or Modifying the Study

Adverse event and laboratory data from this trial will be assessed by the lead site or the sponsor's medical monitor on an ongoing basis. At least quarterly, data from the clinical database will be reviewed. The results of this review will be shared with all investigators either in writing or as part of a teleconference. SAEs will be reviewed as they are reported to the lead site/sponsor, and the medical monitor will make an assessment regarding the safety of continuing or modifying the study. This assessment will be shared with the investigators either in writing or as part of a teleconference. Should the assessment of either the lead site/sponsor or the principal investigator be that the study should be terminated, the study will be closed to further accrual. Patients who are receiving enzalutamide will be assessed individually by the investigator to see if it is in the patients' best interest to continue, which might be the case for a patient that is responding to the intervention. Follow-up safety assessments will be performed for all patients who are terminated from the study prematurely.

APPENDIX A: PERFORMANCE STATUS CRITERIA

ECOG Performance Status Scale		Karnofsky Performance Scale	
Grade	Description	%	Description
0	Normal activity. Fully active, able to continue all predisease performance without restriction.	100	Normal, no complaints, no evidence of disease
		90	Able to carry on normal activity, minor signs or symptoms of disease
1	Symptoms, but ambulatory. Restricted in physically strenuous activity but ambulatory and able to carry out work of a light or sedentary nature (eg, light housework, office work).	80	Normal activity with effort, some signs or symptoms of disease
		70	Cares for self, unable to carry on normal activity or to do active work
2	In bed < 50% of the time. Ambulatory and capable of all self-care but unable to carry out any work activities. Up and about more than 50% of waking hours.	60	Requires occasional assistance but is able to care for most needs
		50	Requires considerable assistance and frequent medical care
3	In bed > 50% of the time. Capable of only limited self-care, confined to bed or chair > 50% of waking hours.	40	Disabled, requires special care and assistance
		30	Severely disabled, hospitalization indicated. Death not imminent.
4	100% bedridden. Completely disabled, cannot carry on any self-care, totally confined to bed or chair.	20	Very sick, hospitalization indicated. Death not imminent.
		10	Moribund, fatal processes progressing rapidly
5	Dead	0	Dead

APPENDIX B: MEDICATIONS WITH THE POTENTIAL FOR DRUG-DRUG INTERACTIONS

Class	Agents	Class	Agent
Drugs that Inhibit CYP2C8	gemfibrozil	Drugs that are metabolized by CYP3A4	alfentanil, cyclosporine, dihydroergotamine, ergotamine, fentanyl, pimozide, quinidine, sirolimus and tacrolimus
Drugs that Induce CYP2C8	rifampin	Drugs that are metabolized by CYP2C19	S-mephenytoin
Drugs that Inhibit CYP3A4	itraconazole)	Drugs that are metabolized by CYP2C9	phenytoin, warfarin
Drugs that Induce CYP3A4	carbamazepine, phenobarbital, phenytoin, rifabutin, rifampin, rifapentine, bosentan, efavirenz, etravirine, modafinil, nafcillin	Substrates for efflux transporter P-gp	colchicine, dabigatran etexilate, digoxin
Substrates for BCRP, MRP2 or OAT3	methotrexat		

